#### **For Aim 2-Procedures for In-depth Interviews.**

We will randomly select a sub-set of intervention group caregivers for semi-structured telephone interviews regarding workshop implementation characteristics. We will sample for caregivers (n=60 total) from all US regions (n=15 per region—West, Midwest, South, Northeast) to achieve the expected saturation of themes within 12-15 interviews/region.

In the 30-minute telephone interview we will probe for deeper understanding of the caregiver's impressions of and responses to the workshop. Interviews will be audiorecorded and electronically stored on secure computers. Following each interview, the interviewer will write a summary of the content of the interview to assist with subsequent analysis of audiorecordings. Professionals will transcribe and anonymize recordings.

Interviewers will ask caregivers questions about workshop Implementation and Maintenance (e.g., What helped you be able to participate in the workshop? Are there other things that would have made it easier for you?, What got in the way of your participation in the workshop? Can you describe things that would help you overcome these problems?, What workshop activities did you participate in and why did you? What activities did you not participate in and why not?, What aspects of the workshop most impacted your caregiving? What workshop lessons or skills have you continued to use?, Can you describe the impact the workshop has had on you or your partner?).

#### **For Aim 1 and 2-Procedures for Learning Collaborative.**

We will establish a Learning Collaborative for our participating community organizations. The Learning Collaborative will enable efficient collection of implementation data, while simultaneously promoting regional and national networking and peer-to-peer learning among organizations serving similar populations of rural caregivers and PWD. Activities will span Years 1-5.

The Learning collaborative will consist of biannual 90-minute webinars and a longitudinal list-serve to promote discussion and information exchange. All webinars will have a similar structure. [name] will facilitate these. The first half will be devoted to a discussion of aspects of workshop implementation. We also will track the use of different outreach strategies and subsequent successful (or unsuccessful) recruitment to inform future implementation efforts. The second half of the webinars will include lectures on and discussion of caregiving and Alzheimer's disease topics relevant to the organizations. Organizations will be invited to nominate topics and speakers during study Year 1 and on an ad hoc basis subsequently. Some webinars may be audio recorded for note purposes.

In addition, members will use a list-serve for learning from each other (e.g., discussing challenges, exchanging tips). Periodically, the research team will make posts to the list-serve to prompt group discussion of specific implementation questions, concerns, or success stories. We will also ask for descriptive data related to their organization.

**8.12 INSTRUMENTS: List all questionnaires, surveys, interview, or focus group guides that will be used for this study:**

**If the instruments are not complete or not available because they will be developed as part of this study, describe the basic content or include an outline and submit the final versions to the IRB with a modification for approval prior to use.**

**Aim 1 Instrument.**

Descriptive variables.

- Baseline questions will ask about caregiver and patient with dementia (PWD) demographic information (e.g., age, gender, race/ethnicity, education);
- caregiving relationship to PWD (e.g., spouse, child),
- resources participants are accessing (e.g., paid in-home care).
- caregiver and PWD chronic conditions (e.g., using the Charlson comorbidity index),
- PWD need for assistance with Activities of Daily Living (ADLs) and Instrumental Activities of Daily Living (IADLs),
- PWD dementia characteristics (e.g., diagnosis, length of diagnosis, degree of impairment, presence of behavioral symptoms).

Primary outcomes.

- Caregivers describe high personal stress as one of the most challenging aspects of being a caregiver. We will use a single-item visual numeric scale (range 1-10) developed by our team. Visual numeric scales [VNS] have been shown to correlate well [ $r = .72$ ] with same-worded visual analogue scales [VAS] and generate higher completion rates.
- We will measure the co-primary outcome of caregiver depression symptoms with an 8-item modified and validated version of the PHQ-9.

Secondary outcomes.

- Self-efficacy will be measured with the 15-item Caregiver Self-Efficacy scale.
- Caregiving burden will be assessed with the 12-item short form of the Zarit Burden Inventory.
- The modified 13-item Caregiver Strain Index will measure caregiver strain.
- Single-item caregiver-reported data will be collected on caregiver and PWD global health, hospitalizations, and emergency room visits.
- We will use the National Health and Nutrition Survey question on global health.
- We will measure healthcare utilization using single-item questions on hospitalizations and emergency room visits that have been demonstrated in multiple studies to be reliable within the 6-month recall time frame we are using, including among dementia caregivers.

**For intervention arm only:** We will embed implementation questions administered to all intervention group caregivers at baseline and months 1.5, 6, and 12. Questions will ask about various aspects (e.g., how heard about trial, reasons for participation, ease of/barriers to logging into workshop and performing online activities, whether completed the workshop and, if not, why not; whether workshop experiences have continued to influence their self-care or caregiving practices or own/partner's health).

**Fidelity monitoring assessment.** We will use the fidelity assessment instrument from pilot studies to evaluate online recordings on a weekly basis for the intervention group. Similarly, we will use a fidelity assessment instrument to evaluate phone calls for the attention control group.

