**For Aim 1-Procedures for RCT.**

Only #1 below will be done if a potential participant does not enroll in the study.

1. **Eligibility:** Eligibility will be determined by an anonymous online screening survey. Potential participants will also be given the option to complete it by mail or phone, if they prefer. Potential participants will be asked their age, gender, to indicate the outreach effort(s) they are responding to in which targeted rural communities, followed by the eligibility criteria: caring for patient with dementia (PWD); able to read and write in English; able to access the internet; providing care for  $\geq 10$  hours per week.

2. **Informed consent:** After confirming eligibility they will read all consent forms (written at the 6th grade level) online. These will be formatted so that they can print them out if desired. They will be offered the opportunity to discuss the study by email or phone with the study coordinator or PI. Those comfortable doing so will then complete the online consent form (or a mailed hardcopy, if they prefer).

3. **Randomization.** Caregivers will be randomized after completion of enrollment and the baseline survey (see4a). Staff will inform study participants about treatment assignment by e-mail or telephone (according to caregiver preference). Caregivers will be randomized to 6-week intervention or attention control group.

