b. **Attention control group.** Participants will receive written materials on dementia and caregiver resources and two brief phone calls of 15-30 minutes apiece by research staff. Caregivers in the attention control group will be offered the online workshop after the 12 month trial is completed if they so desire. The written materials and phone call guides are still under development and will be submitted to the IRB for review as a modification request.

**For control group fidelity purposes.** Phone calls will be recorded. [name] and the research coordinator will evaluate recordings using a fidelity assessment instrument. Staff who stray from the phone call protocol will receive immediate remedial training. If an RA strays from the protocol again, he/she will be removed from making phone calls. At the outset of the trial, fidelity assessment will occur approximately every 4-5 calls to assure fidelity patterns are quickly established and reinforced. Subsequent checks will occur every 10-12 calls.

5. **Assessments:** Data will be collected at baseline, 1.5 months (post intervention), 6 months, and 12 months. Data will be collected through online surveys completed by caregivers and conducted at baseline, post-intervention (1.5 months), and 6, and 12 months using the secure REDCap application. Assessments are expected to be 20 minutes each. Participants will be given the option to complete surveys by mail or phone interview.

a. **Baseline** questions will ask about caregiver and PWD demographic information (e.g., age, gender, race/ethnicity, education); caregiving relationship to PWD (e.g., spouse, child), and resources participants are accessing (e.g., paid in-home care). Baseline questions also will identify caregiver and partner chronic conditions (e.g., using the Charlson comorbidity index), partner need for assistance with ADLs and IADLs, and dementia characteristics (e.g., diagnosis, length of diagnosis, degree of impairment, presence of behavioral symptoms). Caregiver (CG) stress level (Stress visual numeric scale), CG depression symptoms (PHQ-8 score), Self-efficacy (Revised Scale for Caregiver Self-efficacy), Burden (Zarit Burden Inventory), Strain (Caregiver Strain Index), Global health score, and Healthcare utilization items.

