b. **1.5 months.** We will administer the Caregiver (CG) stress level (Stress visual numeric scale), CG depression symptoms (PHQ-8 score), Self-efficacy (Revised Scale for Caregiver Self-efficacy), Burden (Zarit Burden Inventory), Strain (Caregiver Strain Index), Global health score, and Healthcare utilization items. For participants randomized to the

intervention group will be given additional questions on Reach (e.g., how heard about trial, reasons for participation); Implementation (e.g., ease of/barriers to logging into workshop and performing online activities, whether completed the workshop and, if not, why not); and Maintenance (e.g., whether workshop experiences have continued to influence their self-care or caregiving practices or own/partner's health).

c. **6 months.** We will administer the Caregiver (CG) stress level (Stress visual numeric scale), CG depression symptoms (PHQ-8 score), Self-efficacy (Revised Scale for Caregiver Self-efficacy), Burden (Zarit Burden Inventory), Strain (Caregiver Strain Index), Global health score, and Healthcare utilization items. For participants randomized to the intervention group will be given additional questions on Reach (e.g., how heard about trial, reasons for participation); Implementation (e.g., ease of/barriers to logging into workshop and performing online activities, whether completed the workshop and, if not, why not); and Maintenance (e.g., whether workshop experiences have continued to influence their self-care or caregiving practices or own/partner's health).

d. **12 months.** We will administer the Caregiver (CG) stress level (Stress visual numeric scale), CG depression symptoms (PHQ-8 score), Self-efficacy (Revised Scale for Caregiver Self-efficacy), Burden (Zarit Burden Inventory), Strain (Caregiver Strain Index), Global health score, and Healthcare utilization items. For participants randomized to the intervention group will be given additional questions on Reach (e.g., how heard about trial, reasons for participation); Implementation (e.g., ease of/barriers to logging into workshop and performing online activities, whether completed the workshop and, if not, why not); and Maintenance (e.g., whether workshop experiences have continued to influence their self-care or caregiving practices or own/partner's health).

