**8.26 STATISTICAL METHODS: Briefly summarize the methods and types of analyses that will be performed:**

**Aim 1 Data Analysis Methods.**

**Descriptive analyses.** Caregiver and caregiver-reported partner socio-demographic characteristics, chronic conditions, and health utilization outcomes will be summarized as means ( $\pm$ SD), frequencies, percentages, and 95% confidence intervals at baseline and 1.5, 6, and 12 months. The distributions of covariates at baseline will be checked for balance between the two groups with histograms and/or boxplots.

**Primary analyses.** Primary analyses will compare caregiver stress (stress score) and depression symptoms (PHQ-8 score) between intervention and control groups over time with respective linear mixed effects models. Linear mixed effects models use all available observations in the data, assume data are missing at random, and provide an intention-to-treat analysis. Models will include group, time, and (group\*time) interaction terms as fixed effects and community organizations and subjects as random effects to account for the correlation within organizations and subjects due to measurements over time. Covariates with imbalanced distributions between the two groups will also be included in the models to control for potential confounding. The (group\*time) interaction term will be used to evaluate if the two groups differ in outcomes over time. The study is powered to allow 30% loss to follow up. To assess for potential differential withdrawal between groups, comparisons of withdrawal rates and time to withdrawal will be performed. Models based on a potential outcome framework will be used to assess treatment effect while accounting for noncompliance and missing data and to examine potential treatment mechanisms/pathways via intermediate variables (such as social support, self-efficacy, caregiving skills). Multiple imputation based on reasonable assumptions on mechanisms of missing data will be used to perform sensitivity analyses.

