**Secondary analyses.** Secondary analyses will use (generalized) linear mixed effect models similar to the primary mixed effect models for continuous, categorical, and count secondary outcomes. Treatment effects in subgroups (e.g. by sex) of our interest will be evaluated using (generalized) linear mixed effect models with corresponding interactions of group, time and sex while controlling for false discovery rate. We expect a small and balanced recall error between the two groups but if recall error is unbalanced, measurement error models will be considered for treatment evaluation. We will examine loss to follow-up by comparing caregivers lost to follow-up to those who complete the study.

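### The only recall frame stated for hospital and ER use is 6 months, so at the 1.5-month survey 75% of the window would precede randomization

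*Combined protocol and SAP*

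**What the plan says.** All references are to the combined protocol and SAP.

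- **Recall frame.** Section 8.12 (Aim 1 Instrument, secondary outcomes) describes the hospitalization and emergency room questions as "reliable within the 6-month recall time frame we are using". No other recall frame appears in either document.
- **Items.** The same section states: "Single-item caregiver-reported data will be collected on caregiver and PWD global health, hospitalizations, and emergency room visits".
- **Schedule.** Section 8.10, item 5 (Assessments): "Data will be collected at baseline, 1.5 months (post intervention), 6 months, and 12 months". The baseline list ends with "Global health score, and Healthcare utilization items". The 1.5-month list ends in the same way, with "Strain (Caregiver Strain Index), Global health score, and Healthcare utilization items", and the 6- and 12-month lists repeat it. Nothing distinguishes the 1.5-month items from the others.
- **Randomization.** Section 8.10, item 3: "Caregivers will be randomized after completion of enrollment and the baseline survey".
- **Analysis.** Section 8.26 summarizes utilization "at baseline and 1.5, 6, and 12 months". For secondary outcomes in general it states: "Secondary analyses will use (generalized) linear mixed effect models similar to the primary mixed effect models for continuous, categorical, and count secondary outcomes". The primary models have group, time and their interaction as fixed effects, and community organization and subject as random effects.
- **Recall in the analysis.** Section 8.26 considers measurement error models if recall error turns out to be unbalanced between groups. It does not mention windows that overlap or differ in length.

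**The concern.** A fixed 6-month look-back suits surveys that are six months apart. The 1.5-month survey comes only six weeks after baseline, so the same look-back reaches well behind randomization. Events from that earlier period cannot reflect the intervention, yet they would make up most of what is reported at 1.5 months.

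Two things follow. The 1.5-month group contrast in utilization is pulled toward no effect, and a reader of the visit-by-visit summaries could take this as absence of an early effect. If the 1.5-month values also enter a repeated-measures model, neighbouring visits share part of their observation period. This creates a correlation that the planned random-effects structure was not built to describe.

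At stake is the early time point of one listed secondary outcome.

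**Working it through.** The plan gives no figure for overlap, so there is none to reproduce. The check is interval arithmetic on the stated frame and schedule.

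**Inputs.** Recall length R = 6 months (section 8.12); visits at v = 0, 1.5, 6 and 12 months (section 8.10); randomization after the baseline survey (section 8.10).

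**Step 1: windows.** The window at visit v runs from v − 6 to v, in months from baseline.

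| Visit | Window | Share before baseline = max(0, 6 − v)/6 |
|---|---|---|
| Baseline | −6 to 0 | 100% (as intended) |
| 1.5 months | −4.5 to 1.5 | 4.5/6 = 75% |
| 6 months | 0 to 6 | 0% |
| 12 months | 6 to 12 | 0% |

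**Step 2: overlaps.**
- Baseline with 1.5 months: −4.5 to 0, which is 4.5 months.
- 1.5 months with 6 months: 0 to 1.5, which is 1.5 months, or 1.5/6 = 25% of the 6-month window.
- Every other pair: 0.

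Since 4.5 + 1.5 = 6, every month asked about at 1.5 months is also covered by the baseline or the 6-month survey.

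**Step 3: sensitivity to timing.** Suppose the workshop starts two weeks after baseline and the survey falls at about 2 months (an assumption). The pre-baseline share is then (6 − 2)/6 = 67%, and the overlaps are 4 and 2 months. The conclusion does not depend on exact timing.

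**Step 4: dilution, as an illustration.** Assume that the outcome is an event count, that the underlying rate is the same before and after baseline, and that the full effect acts from baseline. The expected ratio at 1.5 months is then

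(4.5 + 1.5 × RR)/6 = 0.75 + 0.25 × RR.

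| True rate ratio after baseline | Ratio seen at 1.5 months |
|---|---|
| 0.70 | 0.925 |
| 0.80 | 0.95 |
| 0.90 | 0.975 |

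An effect that builds up over the six-week workshop would be diluted further.

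**Step 5: correlation, as an illustration.** For Poisson counts at a constant rate with no treatment effect (an assumption), shared events alone give a correlation of overlap/6: 4.5/6 = 0.75 for baseline with 1.5 months, 1.5/6 = 0.25 for 1.5 with 6 months, and 0 for the other pairs. A subject random intercept represents one shared level of association across visits, so it cannot represent this pattern.

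**The case against.** The strongest objection is that the survey form is not in the documents. Reliability within a 6-month frame could mean recall of up to six months, which is the longest gap between surveys, and the 1.5-month form might then ask about a shorter period. This stands as a limit on certainty. It does not remove the point, because the plan states one frame and no exception. A 1.5-month window would also be a quarter of a 6-month one (1.5/6), so the visit summaries would not be comparable, and no exposure time or offset is specified.

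A second objection is that section 8.4 places the main comparison at 12 months, and utilization is not part of the hypothesis or the sample-size basis. This also stands, and it limits the importance of the point.

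A third is that the plan already provides for recall error. That does not help: the overlap would remain even if every participant recalled perfectly.

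A reader might infer more than the documents support:
- **That events are counted twice in a total.** Nothing in the plan sums events across visits; each visit has its own value.
- **That utilization is certainly modelled as a count.** Section 8.26 covers continuous, categorical and count outcomes without saying which type utilization is. A single item could be yes/no.
- **That the 6- or 12-month contrasts are biased.** On the stated frame, neither window contains time before baseline. The correlation problem arises only if the 1.5-month values enter the model, and no bias in the later contrasts has been shown.
- **That 0.95 is a prediction.** It is an illustration under the assumptions in the working.

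**Conclusion.** The point holds for the 1.5-month utilization data, read as the plan is written. With a 6-month frame, 75% of that window precedes randomization and repeats the baseline window, and the remaining 25% is covered again at 6 months. The contrast at that visit is diluted toward no effect and adds no period that another survey does not already cover.

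The 75% rests only on the stated frame and the nominal schedule. The size of the dilution rests further on a constant rate and an immediate full effect. The concern about correlation is conditional on the 1.5-month values being modelled together with the other visits.

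The co-primary outcomes, the sample size and the 12-month utilization comparison are not affected. The point is modest in weight, but following the plan as it stands would produce an early contrast that says little, and correcting it costs little.

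**What to change.** Either of two changes would settle it.

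1. **Drop the visit.** Remove the utilization items, for caregiver and person with dementia alike, from the 1.5-month survey, or keep them and exclude that visit from the utilization analysis. Compare groups on the 6- and 12-month windows and keep baseline as the pre-randomization measure. These three windows adjoin exactly.
2. **Change the window.** Ask about the period since the last completed survey. With no missed surveys the follow-up windows are 1.5, 4.5 and 6 months, which sum to 12 without overlap or pre-baseline time. If the outcome is a count, use the log of each participant's actual months covered as an offset. This has to be individual: someone who missed the 1.5-month survey would report on 6 months, not 4.5, at the next one.

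If the 1.5-month form already uses a shorter window, the plan should state it in section 8.12 and say in section 8.26 how the unequal exposure is handled.

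The cost is a small edit to one survey, or to the item wording, plus a sentence in the analysis plan. Under the first option the 1.5-month utilization estimate is lost; under the second it rests on a short window with correspondingly few events. The first option also shortens the survey if the items are removed.

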**Aim 2 Instrument.**

We will develop an instrument that will be administered to a randomly selected sub-set of intervention group caregivers for semi-structured telephone interviews regarding workshop implementation characteristics. We will probe for deeper understanding of the caregiver's impressions of and responses to the workshop. This instrument will ask caregivers questions about workshop *Implementation* and *Maintenance*. *Implementation* (e.g., ease of/barriers to logging into workshop and performing online activities, whether completed the workshop and, if not, why not) and *Maintenance* (e.g., whether workshop experiences have continued to influence their self-care or caregiving practices or own/partner's health).

